16.3.2. Missing Data Methods for Other Secondary Efficacy Variables

All subjects with missing data, regardless of reason for missingness, will be considered as nonresponders. The intercurrent events that are considered in the primary efficacy analysis will be handled similarly for the other secondary efficacy endpoints, as specified in Section 16.1.2.

16.3.3. Analysis of Other Secondary Efficacy Variables

The analysis of other secondary efficacy endpoints will be performed for the FAS with Baseline MMS 5 to 9. The primary analysis method planned for the primary endpoints in Section 16.1.3 will be repeated for each other secondary efficacy endpoint. No multiplicity adjustment will be made.

will be analyzed using the stratified CMH model described in Section 16.1.3 for the FAS with Baseline MMS 5 to 9.

17.1. Variables and Derivations

17.1.1. Inflammatory Bowel Disease Questionnaire

The Inflammatory Bowel Disease Questionnaire (IBDQ) is a 32-item self-administered questionnaire which has 4 dimensions: bowel symptoms (10 items), systemic symptoms (5 items), emotional health (12 items), and social function (5 items). Responses are graded on a 7-point Likert scale where 7 denotes “not a problem at all” and 1 denotes “a very severe problem”. Scores range from 32 to 224, a higher score indicates better quality of life.

The IBDQ total score and 4 domain subscores are derived on the eCRF directly. Details about scoring rules can be found in [Appendix 4](#).

17.1.2. 36-Item Short Form Health Survey, Version 2

The 36-Item Short Form Health Survey (SF-36) is a 36-item, subject-reported survey of subject health. The SF-36 consists of 36 questions measuring 8 health domains: Physical functioning, bodily pain, role limitations due to physical problems, role limitations due to emotional problems, general health perceptions, mental health, social function, and vitality. The subject’s responses are solicited using Likert scales that vary in length, with 3 to 6 response options per item. The SF-36 will be scored using 2 overall summary scores: Physical component summary and mental component summary scores. A higher score indicates better health status.

The Physical Component Summary Score (norm-based), the Mental Component Summary Score (norm-based), 8 domain subscores (0 to 100 based), and the SF-6D health utility index score are derived by Optum and integrated into the SF-36 eCRF. Details about scoring rules and derivations of domain scores can be found in [Appendix 5](#).

17.1.3. Work Productivity and Activity Impairment Questionnaire – Ulcerative Colitis

The Work Productivity and Activity Impairment Questionnaire – Ulcerative Colitis (WPAI-UC) consists of 6 questions asking about the effect of UC on the subject’s ability to work and perform regular activities.

The percent work time missed due to problem (absenteeism), percent impairment while working due to problem (presenteeism), percent overall work impairment due to problem, and percent activity impairment due to problem are derived on the eCRF directly. Details about derivations can be found in [Appendix 6](#).

17.1.4. Urgency Numeric Rating Scale

The urgency NRS is a single item that measures the severity for the urgency (sudden or immediate need) to have a bowel movement in the past 24 hours using an 11-point NRS ranging from 0 (no urgency) to 10 (worst possible urgency).

17.1.5. Abdominal Pain NRS

The abdominal pain NRS is a single item that measures the “worst abdominal pain in the past 24 hours” using an 11-point NRS ranging from 0 (no pain) to 10 (pain as bad as can imagine).

17.1.6. UC-Related Hospitalizations and Surgeries

The UC-related hospitalizations are captured on the Adverse Events eCRF. The UC-related surgeries, including colectomy, are captured on the Non-Drug Treatment eCRF. Blinded review of AE preferred terms will be performed to determine UC-related hospitalizations.

17.2. Missing Data Methods

No missing data will be imputed for HRQoL endpoints.

18. SAFETY OUTCOMES

All outputs for safety outcomes will be based on the Safety Set. There will be no statistical comparisons between the treatment groups for safety data, unless otherwise specified.

18.1. Adverse Events

AEs will be coded using MedDRA (v24.1). The version used to code AEs will be displayed in the analyses. Treatment-emergent adverse events (TEAEs) are defined as AEs that started or worsened in severity on or after the first dose of study treatment.

Refer to [Appendix 2](#) for handling of partial dates for AEs for the purpose of assigning treatment-emergent flags. In the case where it is not possible to define an AE as treatment-emergent or not, the AE will be classified as treatment-emergent.

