- Subjects with certain cardiac risks will also be excluded from the study. Randomized subjects will be monitored in a period following dosing, and vital signs will be assessed for determination of the subject's health before discharge. Subjects requiring follow-up monitoring will be evaluated in the clinic until cardiac variances return to acceptable levels.

Based on the preclinical and clinical data that has been generated from etrasimod studies and the precautions outlined above, the favorable benefit/risk assessment justifies the further clinical development of etrasimod in subjects with moderately to severely active UC and the current Phase 3 study.

The current study is a Phase 3 multicenter, randomized, double-blind, placebo-controlled study to evaluate the efficacy and safety of etrasimod in subjects with moderately to severely active UC. Subjects who complete the total 52-week treatment or subjects with worsening disease after the Week 12 visit assessments (Section 5.1.1) will have the opportunity to enroll into an open-label extension (OLE) study that will provide additional information on the long-term efficacy and safety of etrasimod. The results from this study will be used to support the regulatory approval of etrasimod for the treatment of patients with UC.

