9.5. Follow-Up Period

For subjects not participating in the OLE study, a follow-up visit, will be performed at 2 and 4 weeks after the last administration of study treatment as indicated in the Schedules of Assessments (Table 7 and Table 8).

If the ET or Study Completion visit is ≥ 2 weeks after the last administration of study treatment, the 2-Week Follow-Up visit is not required; however, the 4-Week Follow-Up visit should be

scheduled and completed. If the ET or Study Completion visit is ≥ 4 weeks after the last administration of study treatment, the 4-Week Follow-Up visit is not required.

If the absolute peripheral lymphocyte count is not within normal limits at the 4-Week Follow-Up visit, subjects should return for CBC with differential according to local standard of care (captured as subsequent Follow-Up visit or unscheduled visit).

All adverse events should be recorded for 30 days after last administration of study treatment (Section 9.10.8.2.2).

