9.10.8.2.2. Recording Adverse Events

The adverse event reporting period for safety surveillance begins when the subject is initially included in the study (date of first signature of informed consent) and continues up to 30 days after the last administration of study treatment. If an adverse event is not resolved or stabilized by this time, the Sponsor in consultation with the Investigator will decide whether to continue to monitor the adverse event or closeout the event in the database if no further follow-up is necessary.

Any SAE suspected to be related to the study treatment must be reported whenever it occurs, irrespective of the time elapsed since the last administration of study treatment.

Investigators and study personnel will record all adverse events and SAEs whether received through an unsolicited report by a subject, elicited during subject questioning, discovered during physical examination, laboratory testing, and/or other means by recording them on the eCRF and/or SAE Form, as appropriate. The following information should be recorded on the adverse event eCRF:

- Description including onset and resolution dates
- Whether it met SAE criteria
- Severity
- Relationship to study treatment or other causality
- Outcome

For SAEs, events occurring secondary to the primary event should be described on the eCRF in the narrative description field.

The following should be considered when recording SAEs:

- Death is an outcome of an event. The event that resulted in the death should be recorded and reported on the eCRF.
- For hospitalizations, surgical, or diagnostic procedures, the illness leading to the surgical or diagnostic procedure should be recorded as the SAE, not the procedure

itself. The procedure should be captured in the narrative as part of the action taken in response to the illness.

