- ^p All concomitant medications and procedures should be collected through the safety reporting period (Section 6.7). For subjects receiving corticosteroid therapy during the 12-Week Treatment Period, corticosteroids should be tapered for subjects entering the 40-Week Treatment Period (Section 6.7.2.2).
- ^q The QuantiFERON TB Gold and tuberculin skin test should not be performed in subjects previously diagnosed with TB infection. For subjects who are receiving TB prophylaxis treatment, the TB questionnaire will be completed at every study visit (until TB prophylaxis treatment course is completed).
- ^r Study treatment should be dispensed as indicated. For subjects who consent and are eligible for the APD334-303 OLE study prior to Week 52, double-blinded study treatment may be dispensed in the event there is a gap between the last on treatment visit of the parent study and W0/D1 of the OLE. Study treatment may be dispensed at Week 52 if the subject qualifies for and has opted to participate in the APD334-303 OLE study but who do not enter the OLE study on the same day as their Week 52 visit.
- ^s On days with scheduled study visits, subjects should not take their dose of study treatment at home in order to complete pre-dose study procedures. The dose will be taken at the study site after all pre-dose assessments and procedures have been completed.

AV, atrioventricular; β-hCG, beta-human chorionic gonadotropin; BP, blood pressure; CBC, complete blood count; D, day; DLCO, diffusing capacity of the lungs for carbon monoxide; eDiary, electronic diary; EIM, extraintestinal manifestations; FEV₁, forced expiratory volume at 1 second; FVC, forced vital capacity; HR, heart rate; hs-CRP, high-sensitivity C-reactive protein; IBDQ, Inflammatory Bowel Disease Questionnaire; MMS, modified Mayo score; NRS, numeric rating scale; OCT, optical coherence tomography; OLE, open-label extension; PGA, Physicians Global Assessment; PK, pharmacokinetics; RB, rectal bleeding; SF, stool frequency; SF-36, Medical Outcomes Study 36-Item Short Form Health Survey; TB, tuberculosis; UC, ulcerative colitis; UC-PRO/SS, Ulcerative Colitis Patient-Reported Outcomes Signs and Symptoms; W, week; WHO, World Health Organization; WPAI UC, Work Productivity and Activity Impairment Questionnaire – Ulcerative Colitis

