18.1.5. TEAEs of Special Interest

Categories of Targeted Medical Events (TMEs) and a list of preferred terms associated with these TME categories were developed based on the mechanism of action of etrasimod, prior experience with other agents acting via a similar mechanism, and disease-specific clinical judgment. In addition, where standard testing has been implemented to screen for potential AESI (eg, electrocardiograms, spirometry, serum transaminases, etc.), the relevant data will be reviewed to identify potential cases of AESI that investigators may not have identified and to provide quantitative data for AESIs. The proposed candidate terms will be reviewed to identify which events reflect AESI.

TEAEs of special interest will be summarized by category, subcategory, and PT by descending frequency by treatment group. Categories and subcategories of TEAEs of special interest are the following:

- Cardiovascular Events
 - Bradycardia
 - AV conduction delay
 - Hypertension
- Macular Edema
- Pulmonary Disorders
 - Airflow obstruction (forced expiratory volume in 1 second [FEV₁], forced vital capacity [FVC])
 - Decrease gas exchange (diffusing capacity of the lungs for carbon monoxide [DLCO])
- Infections
 - Severe infections
 - Opportunistic infections (Narrow)
 - Herpes simplex and herpes zoster

- Liver Injury
 - Liver transaminases elevation
 - Bilirubin elevation
- Posterior Reversible Encephalopathy Syndrome (PRES)
- Malignancies

For each category, subcategory, and PT, model-based analysis will be performed to compare treatment effect between etrasimod and placebo. An extended Cox regression model will be used to handle recurring AEs (Cao 2011). The stratification variables, naïve to biologic or JAK inhibitor therapy status at study entry (Yes or No), Baseline corticosteroid use (Yes or No), and Baseline disease activity (MMS: 4 to 6 or 7 to 9), will be included in the model. A subject with K events contributes (K+1) observations to the input data set; here K might be 0. The k-th observation of the subject identifies the time interval from the start date of the (k-1)-th event, or time 0 (if k = 1), to the start date of the kth event, k = 1, ..., K. The (K+1)-th observation represents the time interval from the K-th event to the date of censorship, ie, the date of last dose or date of last study visit up to Week 52, whichever is later. Hazard ratios, 95% CIs, and p-values for treatment effect comparison will be presented.

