APPENDIX 2: PARTIAL DATE CONVENTIONS

Imputed dates will NOT be presented in the listings.

ALGORITHM FOR TREATMENT EMERGENCE OF ADVERSE EVENTS:

AE Start Date	AE Stop Date	Action
Known	Known, Partial, or Missing	If AE start date < study treatment first dose date, then not TEAE If AE start date ≥ study treatment first dose date, then TEAE
Partial, but known components show that it cannot be on or after date of first dose of study treatment	Known, Partial, or Missing	Not TEAE
Partial, could be on or after date of first dose of study treatment	Known	If AE stop date < study treatment first dose date, then not TEAE If AE stop date ≥ study treatment first dose date, then TEAE
	Partial	Impute AE stop date as latest possible date (ie, last day of month if day unknown or 31st December if day and month are unknown), then: If AE stop date < study treatment first dose date, then not TEAE If AE stop date ≥ study treatment first dose date, then TEAE
	Missing	Assumed TEAE
Missing	Known	If AE stop date < study treatment first dose date, then not TEAE If AE stop date ≥ study treatment first dose date, then TEAE
	Partial	Impute AE stop date as latest possible date (ie, last day of month if day unknown or 31st December if day and month are unknown), then: If AE stop date < study treatment first dose date, then not TEAE If AE stop date ≥ study treatment first dose date, then TEAE
	Missing	Assumed TEAE

ALGORITHM FOR PRIOR AND CONCOMITANT MEDICATIONS:

Start Date	Stop Date	Action
Known	Known	If medication stop date < study treatment first dose date, assign as prior If medication stop date ≥ study treatment first dose date, assign as concomitant
	Partial	Impute stop date as latest possible date (ie, last day of month if day unknown or 31st December if day and month are unknown), then: If medication stop date < study treatment first dose date, assign as prior If medication stop date ≥ study treatment first dose date, assign as concomitant
	Missing	If medication stop date is missing could never be assumed a prior medication, assign as concomitant
Partial	Known	Impute start date as earliest possible date (ie, first day of month if day unknown or 1st January if day and month are unknown), then: If medication stop date < study treatment first dose date, assign as prior If medication stop date ≥ study treatment first dose date, assign as concomitant

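### The treatment-emergent period has no stated end: events after a switch to open-label etrasimod can be counted under placebo, and the AESI and EAIR time windows do not match the events counted

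*SAP*

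**What the plan says.** SAP 18.1 counts as treatment-emergent all "AEs that started or worsened in severity on or after the first dose of study treatment". The algorithm in SAP Appendix 2 follows suit: "If AE start date ≥ study treatment first dose date, then TEAE". Neither place checks the last dose, a period after it, or entry to the extension.

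Protocol 9.10.8.2.2 says that the reporting period "continues up to 30 days after the last administration of study treatment". Protocol 9.5 repeats it: "All adverse events should be recorded for 30 days after last administration of study treatment". Neither sentence treats subjects who enter APD334-303 differently. Serious events thought to be related have no time limit: "Any SAE suspected to be related to the study treatment must be reported whenever it occurs, irrespective of the time elapsed".

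Subjects of either arm may enter the extension from Week 12 on disease worsening, or at Week 52 (Protocol 3.1 and 5.1.1). Protocol 1.3 describes it as an "open-label extension (OLE) study that will provide additional information on the long-term efficacy and safety of etrasimod". Table 8 footnote r allows blinded drug to bridge to extension Day 1: "double-blinded study treatment may be dispensed in the event there is a gap between the last on treatment visit of the parent study".

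SAP 5.6 analyses the Safety Set by treatment received, with no rule for drug received in the extension. SAP 18.1.5 does set an end for its recurrent-event model: "the date of last dose or date of last study visit up to Week 52, whichever is later". The exposure-adjusted incidence rate (EAIR) in SAP 18.1.1 runs to last participation for subjects without the event, and that term is not defined.

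**The concern.** Because of the bridging supply, the last blinded dose can fall right before the first extension dose. For such a subject nearly all of the 30-day recording period is spent on open-label etrasimod. If an event in that period is recorded in this study, the SAP flags it as treatment-emergent and nothing keeps it out of the column for the blinded arm.

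For effects tied to the first dose, the error would run one way. Protocol 1.3 names first-dose bradycardia and AV block as class effects, and SAP 18.1.5 lists bradycardia and AV conduction delay among the events of special interest (AESIs). A placebo subject meets etrasimod for the first time on extension Day 1, whereas an etrasimod subject has already had the first dose. Misplaced events of this kind would add to placebo only and shrink the differences in the AESI tables and in the risk differences of SAP 18.1.6.

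A second problem does not depend on the extension. The rule for counting an event and the rule for ending time at risk stop at different dates.

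**Working it through.** The documents give no figure for the length of the treatment-emergent window, the rollover rate or events after the switch, so there is nothing to reproduce. Documented inputs are 140 planned placebo subjects (SAP 7), a 30-day recording period (Protocol 9.5 and 9.10.8.2.2), and Week 12 and Week 52 at Days 85 and 365 (Tables 7 and 8). Everything else is an assumption.

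1. **Greatest overlap per rollover subject under the 30-day rule.** Share of the window spent on extension drug = 30 / (days on blinded drug + 30).
   - Switch at Week 12: 30 / (85 + 30) = 26.1%.
   - Switch at Week 52: 30 / (365 + 30) = 7.6%.

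2. **Expected placebo subjects misplaced, per event type** = 140 × r × q × c, where r is the rollover share, q the 30-day event risk on etrasimod, and c the share of such events captured in this study's database. Assume r from 0.25 to 0.75 and q from 0.01 to 0.10.
   - c = 1, low end: 140 × 0.25 × 0.01 = 0.35 subjects (0.25 percentage points).
   - c = 1, high end: 140 × 0.75 × 0.10 = 10.5 subjects (7.5 percentage points).
   - c = 0: none.
   - Etrasimod time inside the placebo window: 140 × 0.25 × 30/365.25 = 2.9 subject-years, up to 140 × 0.75 × 30/365.25 = 8.6.

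3. **Illustration for a first-dose event.** Assume a risk of 2% on etrasimod and 0.2% on placebo. The true difference is 1.8 points; the tabulated difference is 1.8 − 2 × r × c.
   - r = 0.5, c = 1: 1.8 − 1.0 = 0.8 points.
   - r = 0.8, c = 1: 1.8 − 1.6 = 0.2 points.
   - c = 0: 1.8 points, unchanged.

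   This applies only to events concentrated at the first dose. For events with steady risk, etrasimod rollovers add tail events as well. With equal rollover in both arms, the absolute difference then changes little, while rates and ratios are diluted.

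4. **Censoring in SAP 18.1.5, no extension involved.** Take a Week 52 completer who does not roll over, with last dose and last treatment visit on Day 365.
   - An AESI on Day 375 lies inside the recording period, which runs to Day 365 + 30 = 395, and is treatment-emergent under SAP 18.1.
   - The model's censoring date is Day 365.
   - The last record for a subject runs from the last event to censoring: 365 − 375 = −10 days.

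5. **EAIR.** A subject with the event contributes time to onset, here 375 days. A similar subject without it contributes time to last participation. That could mean Day 365 or the 4-week follow-up visit at Day 365 + 28 = 393. The SAP does not choose, so numerator and denominator need not cover the same period.

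**The case against.** The strongest objection is that this reads a rule into silence. APD334-303 is a separate study with its own eligibility and Day 1, and its protocol is not available here. No sentence says that events after the switch are entered in the APD334-301 database. Protocol 9.5 opens with subjects who do not join the extension, and rollovers have no 2-week or 4-week follow-up visit in this study at which such an event would be elicited. This stands, and it is why capture is left open above. It does not close the gap. Protocol 9.10.8.2.2 applies to all subjects, and the drafters did carve out extension entrants for follow-up visits and follow-up PK samples but not for adverse events. SAP Appendix 7 stops classifying rescue therapy at the last dose, so an end date is set where one was wanted.

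Other limits also stand. The recurrent-event model does have an end, which for a typical rollover falls at or before the first extension dose, so applied as written its hazard ratios do not absorb extension time. The negative interval is a drafting fault and is not evidence of contamination. First-dose heart rate and ECG have their own Day 1 summaries in SAP 18.4 and 18.5, which extension events cannot enter, so a first-dose signal would not disappear from the report.

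Finally, a plain 30-day cap for everyone would push late related SAEs in non-rollovers out of the tables and could itself understate risk. The fix has to allow for that.

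**Conclusion.** Two points hold. First, the treatment-emergent definition has no end and neither document assigns events that start after the first extension dose, so early open-label etrasimod events can be counted under placebo and bias first-dose comparisons toward no difference. The size cannot be stated: rollover, event risk and capture are all missing from the documents. The 0.35 to 10.5 subjects per event type rest on assumed rollover and risk with full capture, and the lower limit is zero.

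Second, and independently of the extension, the SAP 18.1.5 censoring date can precede an event that SAP 18.1 counts, and the EAIR denominator has no defined end. This follows from the text without any assumed rate.

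A reader might infer that the plan prescribes counting extension events as placebo events, or that most of a first-dose risk difference would be lost. The documents support neither. The first is permitted by silence but not written. The second comes from the chosen rates in step 3, full capture, and a single event type, and does not carry over to AESIs, SAEs or adverse events in general.

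**What to change.** - In SAP 18.1 and Appendix 2, do not flag as treatment-emergent in this study any event starting on or after the first APD334-303 dose. List such events separately.
- For subjects who do not roll over, end the treatment-emergent and time-at-risk window 30 days after the last dose, matching the recording period. Tabulate later related SAEs reported under Protocol 9.10.8.2.2 separately so that they are not lost.
- Use the same end date for censoring in SAP 18.1.5 and as the definition of last participation in SAP 18.1.1.
- Add one sentence to Protocol 9.10.8.2.2 assigning events after the first extension dose to APD334-303.

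The cost is a few sentences and one derived date, the first extension dose. Rollover subjects lose their nominal post-dose tail. Where bridging supply runs up to extension Day 1, that tail is not off-drug time in any case.
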